4.1 Inclusion Criteria

Participants must meet all of the following inclusion criteria to participate in this study:

- Able and willing to provide written informed consent
- Male or Female, 60 years of age or older
- Willing to receive pneumococcal vaccination with Prevnar 13 (Wyeth/ Pfizer) or Pneumovax 23 (Merck), as randomly assigned.
- Available to attend 6 study visits over 67 days (Visit 7 is optional at Day 365-720).

4.2 Exclusion Criteria

Candidates meeting any of the following criteria will be excluded from study participation:

- Previous pneumococcal vaccination with Prevnar 13 or Pneumovax 23.
- History of anaphylactic/anaphylactoid or severe allergic reaction to any component of Pneumovax 23, Prevnar 13 or any diphtheria toxoid-containing vaccine.
- Established diagnosis of diabetes
- History of receiving Zostavax (shingles vaccine) within previous 4 weeks. (Study entry may be delayed to satisfy a 28-day interval between vaccinations)
- Known history of any of the following co-morbid conditions:
 - Malignancy (participants without a recurrence in the last 5 years will be allowed)
 - Congestive Heart Failure
 - Cardiovascular Disease (unstable \leq 6 months*)
 - Kidney disease

- Renal failure
- Impaired hepatic function
- Autoimmune disease such as: Rheumatoid Arthritis, systemic lupus erythematosus (SLE), Inflammatory Bowel Disease, etc.
- Use of medicines during past 6 months known to alter immune response such as high-dose corticosteroids
- HIV, AIDS or other Immunodeficiency
- Recent (\leq 3 months) trauma or surgery
- Current substance and/or alcohol abuse

* Unstable disease is defined as a change in therapy or hospitalization for worsening disease.

4.3 Study Enrollment Procedures

Forty (40) healthy men and women, ages 60 and older, from all ethnic backgrounds, that have never received pneumococcal vaccination will be recruited to this study over a two-year period.

Recruitment letters will be prepared, approved by IRB and mailed to potentially eligible individuals from the UConn Center on Aging recruitment database that describe the study and provide contact information to obtain more information from a member of the study team. All persons listed in the recruitment database agreed to be contacted about future research projects during prior interactions with the Center on Aging clinical research team. Other recruitment methods may include recruitment flyers placed in local clinics, use of broadcast email in the UConn Health system, newspaper/print advertisements, outreach to collaborating research clinics in urban areas or through physician referrals to the study.

Interested persons will phone the study team in response to the letter, broadcast email, flyer, referral or other advertisement to complete an IRB-approved preliminary screening questionnaire that asks general and aggregated questions to determine eligibility while minimizing collection of Protected Health Information. Progression through the screening questionnaire will stop when a response is given that renders the caller ineligible. Demographic information (age, gender, race, and ethnicity) will be collected for all callers for transparent reporting of participant selection, but individual identifiers and contact information will only be collected after the preliminary screening questionnaire has been successfully completed, indicating preliminary eligibility. A copy of the IRB approved Informed Consent Form (ICF) will be provided to potential subjects for review prior to the informed consent/screening visit, whenever possible. The ICF may be provided by fax, email, interoffice mail, hand delivery or by US Mail. The participant will then be scheduled for Visit 1, when the informed consent process will be initiated and the ICF signed before full screening or any other study procedures are performed.

5 STUDY INTERVENTIONS

5.1 Interventions

For 2015, the CDC revised recommendations for pneumococcal vaccination of adults age 65 and older that have never received pneumococcal vaccination, to include one dose of PPSV23 (Pneumovax 23) and one dose of PCV13 (Prevnar 13). Their recommendation is to administer PCV13 first followed by PPSV23 \geq 1 year later[53]. Although pneumococcal vaccine is recommended for healthy adults to receive at age 65 or older, it is routinely given to children and

adults 2 to 64 years of age, with various chronic disease. Subjects who elect to participate in this study would be receiving the vaccination as a healthy adult, at an earlier age.

While PCV13 demonstrated efficacy in reducing incidence of community acquired pneumonia (CAP) due to serotypes of *S. pneumoniae* included in the vaccine, it did not demonstrate efficacy in community acquired pneumonia from any cause with reported vaccine efficacy of 5.1%, 95% CI, (-5.1 to 14.2) (2). PPSV23 includes 11 serotypes that are not included in PCV13 and elicits immune response by a different mechanism than the conjugated vaccine. Since reduced response to pneumococcal vaccination in patients age 65 and older limits the benefits of vaccination, it is critical to develop additional understanding of aging-related immunosenescence to find ways to increase response to vaccination in this population. Each vaccine has potential benefits and limitations. PCV13 and PPSV23 have not been compared directly for effectiveness in reducing incidence or severity of CAP through a randomized, controlled clinical trial (3). Studies to date have used antibody response as outcome measures rather than clinical efficacy and have focused on the 12 serotypes of *S. pneumoniae* that PPSV23 and PCV13 share. This study looks to develop a deeper understanding of the mechanisms of diminished response to both vaccines in the elderly.

To elucidate transcriptional and epigenetic profiles of the mechanisms of response to each vaccine in the elderly, enrolled participants will be randomly assigned to receive pneumococcal vaccination with **Prevnar-13 (PCV13) or Pneumovax-23 (PPSV23)**. These vaccines are FDA approved for administration in this population and will be administered by a Registered Nurse at the dose and by route (intramuscular injection), as approved.

Randomized assignment to group will be in a 1:1 ratio utilizing block randomization in blocks of 10. A Randomization Plan will be prepared by the Data Manager at the UConn Center for Aging using Randomization software. Randomization assignments will be revealed to the research nurse when the subject meets eligibility for randomization and is assigned the next available sequential randomization number. Participants will receive the vaccine that was randomly assigned to their sequential randomization number in the study and will be offered a boost dose with the non-assigned vaccine one to two years later.

Participants will be informed of the vaccine that was administered and will be provided with information about the vaccine as provided by the manufacturer. Pneumovax 23 has an FDA-approved Patient Product Information Sheet that will be provided to participants receiving Pneumovax 23. Participants that receive Prevnar 13 will receive a Fact Sheet about the vaccine prepared by Pfizer. Each participant will also be given a pneumococcal vaccine fact sheet from CDC for the vaccine administered.

Summary of Prescribing Information for Prevnar 13 and Pneumovax 23 (4, 5) :

	Prevnar-13	Pneumovax-23
Dose	Adults 18 years and older: a single dose 0.5 mL dose.	Adults 50 Single 0.5-mL dose
Route of Administration	Intramuscular injection	Intramuscular injection
Indications	In adults 18 years of age and older, Prevnar 13 is indicated for active immunization for the prevention of pneumonia and invasive disease caused by S. pneumoniae serotypes 1, 3, 4, 5, 6A, 6B, 7F, 9V, 14, 18C, 19A, 19F and 23F.	Pneumovax 23 is approved for use in persons 50 years of age or older. Pneumovax 23 is indicated for active immunization for the prevention of pneumococcal disease caused by the 23 S. pneumoniae serotypes contained in the vaccine (1, 2, 3, 4, 5, 6B, 7F, 8, 9N, 9V, 10A, 11A, 12F, 14, 15B, 17F, 18C, 19F, 19A, 20, 22F, 23F, and 33F)
Contraindications	Severe allergic reaction (e.g., anaphylaxis) to any component of Prevnar 13 or any diphtheria toxoid-containing vaccine.	Severe allergic reaction (e.g., anaphylaxis) to any component of Pneumovax 23.
Limitations of Use and Effectiveness	Prevnar 13 does not protect against disease caused by S. pneumoniae serotypes that are not in the vaccine.	Pneumovax 23 will not prevent disease caused by capsular types of S. pneumoniae other than those contained in the vaccine.
Source	FDA- approved Prescribing Information, Prevnar 13	FDA- approved Prescribing Information, Pneumovax 23

Vaccine Administration

Both Prevnar-13 and Pneumovax 23 will be administered at the dose, by the route and in the population currently approved for marketing by FDA, therefore administered consistent with routine clinical care. Vaccine will be administered by a Registered Nurse using best practices and will be administered by intramuscular injection in the deltoid. Participants will be required

to remain in the clinic for 30 minutes after vaccine administration to be monitored for life-threatening allergic reactions. The nurse will discharge the participant after 30 minutes has elapsed.

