3 STUDY DESIGN

This prospective, single-site, randomized, then open-label study is designed to develop a detailed transcriptional and epigenetic profile of the immune response to pneumococcal vaccination with conjugated and non-conjugated polysaccharide vaccines in the senescent immune system of older adults. This knowledge may lead to development of more effective vaccines through increased understanding of the effects of immunosenescence on mechanisms of immune response to pneumococcal vaccination in the elderly.

Forty (40) healthy adults ages 60 and older that have never received pneumococcal vaccination, will be randomized in a 1:1 ratio to receive Prevnar-13 (Pfizer), a conjugated 13-valent vaccine or Pneumovax 23 (Merck), a non-conjugated 23-valent vaccine. Following randomized assignment of vaccine, the study will be open-label.

The first six (6) study visits are planned to occur over 67 days at Days -7, 0, 1, 10, 28 (± 3 d) and 60 (± 5 d). Participants will provide blood samples for transcriptional, epigenetic and biological analyses pre- and post-vaccination.

One to two years after receiving the randomly-assigned vaccination, participants may opt to receive administration of a second pneumococcal vaccine with the vaccine that they did not receive by random assignment at Visit 2 (Day 0). This second vaccine will be provided at no charge to the participant. Administration of this vaccine will occur at an optional Visit 7 for participants who choose to receive the second vaccine and will be scheduled at the participant's convenience one-two years after receiving the first pneumococcal vaccine.

If the participant opts to receive the second vaccine within the study and attends optional Visit 7, blood samples for genomic and biologic analysis will be collected at the visit.

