- Once the subject has met all eligibility criteria, they are assigned the next available sequential randomization number on the Randomization Log. The PID is entered in

the space next to the number on the Randomization Log and the Randomization number is entered on the Randomization and Vaccination Form for this PID to be used at Visit 2.

- Visit 2 is scheduled 7 days from Visit 1. There is no window for sample collections in this study.

Baseline measures

- Vital signs (blood pressure, heart rate, and respiration rate), weight and height are recorded.
- **Blood draw of 50 mL:** Blood will be collected peripherally by phlebotomy by qualified research staff using best practices. The tubes will be labeled with PID, Visit number and date of collection. Fifty (50) mL will be drawn and securely transferred to JAX-GM for processing and analysis. Three (3) mL will be sent by JAX-GM to Quest Diagnostics Laboratory or to another JAX campus for a complete blood count (CBC) with differential testing for research purposes only. The results of the CBC blood test will be coded with the PID number only and will not be placed in medical records. Results will be sent back to Jackson Laboratory for use in research testing. Results will not be shared with research participants, however, if the study doctor feels that blood sample shows abnormalities during research testing, he may contact participant and advise them to follow-up with their personal physician.

Visit 2: Day 0: Vaccination Visit. Approximate visit time = 15-30 minutes.

At Visit 2, the following procedures will be performed:

Body Temperature and Blood Draw

- Taking and recording of body temperature °F (oral or ear)
If the participant has a body temperature of 100.5°F (38° C) or greater, Visit 2 will be deferred and rescheduled for a minimum of 3 days in the future.

A deferral of vaccination due to fever will not require an additional Visit 1 blood draw 7 days in advance of vaccination as long as vaccination occurs within 14 days of the original Visit 1 blood draw.

Participants with a temperature below 100.5°F will proceed to blood draw.

- **Blood draw of 10 mL:** Blood will be collected peripherally by phlebotomy by qualified research staff prior to vaccination. The tube will be labeled with PID, Visit number and date of collection and will be securely transferred to JAX-GM for processing and analysis.

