- The research nurse reviews the Randomization and Vaccination form and identifies the assigned vaccine from the Randomization Plan for the randomization number.
- The subject is informed of the randomized vaccine assignment and given information about the vaccine.

Data Collection

- Adverse events

- Concomitant medication use

Vaccination

- The research nurse obtains one dose of the assigned vaccine from the refrigerator and prepares the dose per the package insert.
- The vaccine dose label (sticker) is placed in the designated area of the Visit 2 Source Document Form.
- The area of the deltoid where the vaccine will be injected is wiped with alcohol
- The vaccine is injected intramuscularly in the deltoid by the RN.

The participant must remain at the clinic for 30 minutes after vaccine administration to be monitored for life-threatening allergic reactions. Visits are scheduled for study visits 3-6. There is no visit window for follow-up visits. Visits must be performed on the day indicated. The nurse will discharge the participant after 30 minutes has elapsed.

Visit 3: Day 1: Follow-up visit. Approximate visit time = 15 minutes.

Weight, Blood pressure, heart rate, temperature: taken and recorded on source document.

Data Collection

- Adverse events
- Concomitant medication use

Blood Draw

- **Blood draw of 50 mL:** Blood will be collected peripherally by phlebotomy by qualified research staff prior to vaccination. The tube will be labeled with PID, Visit number and date of collection. The sample will be securely transferred to JAX-GM for processing and analysis following the study visit.

Visit 4: Day 10 (\pm 1 day) : Follow-up visit. Approximate visit time = 15 minutes.

Weight, Blood pressure, heart rate, temperature: taken and recorded on source document.

Data Collection

- Adverse events
- Concomitant medication use

Blood Draw

- **Blood draw of 50 mL:** Blood will be collected peripherally by phlebotomy by qualified research staff prior to vaccination. The tube will be labeled with PID, Visit number and date of collection. The sample will be securely transferred to JAX-GM for processing and analysis following the study visit.

Visit 5: Day 28 (\pm 3 days): Follow-up visit. Approximate visit time = 15 minutes.

Weight, Blood pressure, heart rate, temperature: taken and recorded on source document.

Data Collection

- Adverse events
- Concomitant medication use
- Medical History Review and update

Blood Draw

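### The printed block length of 10, open-label treatment and a look-up in the Randomization Plan leave upcoming assignments partly predictable, and the protocol does not say that later lines of the Plan are concealed

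*Combined protocol and SAP*

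**What the plan says.** Section 5.1 gives one block length, with no mention of varying it: "Randomized assignment to group will be in a 1:1 ratio utilizing block randomization in blocks of 10". It names the author of the list: "A Randomization Plan will be prepared by the Data Manager at the UConn Center for Aging using Randomization software". It adds that the nurse learns an assignment once the person is found eligible and has been given the next number in order.

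Section 6.2 places the issue of the number at Visit 1, where eligible subjects are handled as follows: "they are assigned the next available sequential randomization number on the Randomization Log". At Visit 2 the research nurse checks the participant's form and "identifies the assigned vaccine from the Randomization Plan for the randomization number".

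Section 3 describes the setting: "This prospective, single-site, randomized, then open-label study", and "Following randomized assignment of vaccine, the study will be open-label". The size is also there: "Forty (40) healthy adults ages 60 and older that have never received pneumococcal vaccination, will be randomized in a 1:1 ratio". No stratification is described.

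Three other places bear on who could see or use the sequence:

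- Section 5.2 has the pharmacist hand all doses to the research team, so there is no pharmacy release per participant.
- Section 9.3 describes one delegation log that covers both eligibility decisions and vaccine administration. It does not require different people for the two tasks.
- No section describes sealed envelopes, central or database allocation, or hiding of the lines of the Plan not yet used.

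**The concern.** Concealment means that whoever decides who enters next cannot know which arm is next. Here the block length is in the protocol, one team sees every past assignment, and numbers run in order. Towards the end of each block the remaining assignments can therefore be narrowed down and sometimes deduced. The document used to look up the current assignment is also the one that holds the future ones.

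The opportunity to act on this exists. Section 4.3 collects age from all callers during phone screening, before Visit 1 is booked. Accrual is slow, at 40 people over two years. Some exclusion wording in section 4.2 leaves room for judgement, and entry can be deferred for a recent shingles vaccine before a number is issued. A possible motive is also in the text: section 5.1 says of the guideline for never-vaccinated adults of 65 and over, "Their recommendation is to administer PCV13 first followed by PPSV23", while the trial enrols from 60.

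The Aim 1 hypothesis (section 1.1) compares the two vaccines, with 20 people per arm. If the expected vaccine influenced who was booked or judged eligible, age or health could differ between arms for reasons other than chance.

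**Working it through.** The plan gives no figure for predictability, so there is none to reproduce.

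**Inputs.** Blocks of 10, 5 per arm (section 5.1). N = 40, so 40/10 = 4 complete blocks (section 3). One site, open-label (section 3). Seven days from Visit 1 to Visit 2 (section 6.2). Two-year accrual (section 4.3), a mean gap of 730/40 = 18.25 days.

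**Certain assignments, only past assignments known.** A 5+5 block has C(10,5) = 252 equally likely orders. An assignment is certain when all remaining places belong to one arm.

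| Place in block | Orders in which it is certain | Share |
|---|---|---|
| 6th | 2 of 252 | 0.008 |
| 7th | 12 of 252 | 0.048 |
| 8th | 42 of 252 | 0.167 |
| 9th | 112 of 252 | 0.444 |
| 10th | 252 of 252 | 1 |

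The total is 420/252 = 1.67 per block, which agrees with 2m/(m+1) = 10/6 for m = 5. Over four blocks that is 6.7 of 40 (16.7%).

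**Best guess.** The guesser names the arm used less often so far and tosses a coin when the arms are level. Expected correct guesses per block are m + 2^(2m−1)/C(2m,m) − 1/2. For m = 5 this is 5 + 512/252 − 0.5 = 6.53 of 10, or 26.1 of 40 (65.3%). Simple randomisation gives 20 of 40.

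**If the assignment is learned only at Visit 2.** Each assignment then becomes known 7 days after the number is issued. Simulation with uniform arrivals (an assumption; 20,000 runs over 730 days, 8,000 for the shorter periods) gives:

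| Accrual period | Correct guesses | Certain of 40 |
|---|---|---|
| 730 days | 63.6% | 5.3 |
| 365 days | 62.2% | 4.2 |
| 180 days | 59.8% | 2.5 |

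The point therefore does not depend on which visit is meant, although the size falls with faster accrual.

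**Effect of other block schemes on the guess rate.** The same formula, over complete blocks, gives:

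| Scheme | Correct guesses |
|---|---|
| Fixed 4 | 70.8% (33% certain) |
| Mixed 4/6/8 | 68.1% |
| Mixed 6/8/10 | 66.5% |
| Fixed 10 | 65.3% |
| Mixed 8/10/12 | (5.33 + 6.53 + 7.72)/30 = 65.3% |
| Fixed 20 | 61.7% |
| One block of 40 | 58.7% |

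Varying undisclosed sizes removes nearly all the certainty, because the end of a block can no longer be located. It does not lower the average guess rate, because following the running imbalance still works. Small blocks make guessing easier.

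**If later lines of the Plan could be read,** every assignment would be known under any block scheme.

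**The case against.** The strongest reply is that section 5.1 reveals an assignment only when a participant has been found eligible and numbered, which reads naturally as release one at a time. The Log of numbers at Visit 1 is named separately from the Plan, and the look-up comes at Visit 2, after that participant's consent and eligibility. A reader might infer from the look-up that the nurse sees the upcoming vaccines and that all assignments are predictable. The documents do not support that: they neither say that later lines are visible nor that they are hidden. What stands is the gap. A look-up in the Plan is the stated procedure, and nothing limits it to one line.

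The guessing figures are upper values. They need staff who know the block length, follow every assignment and use the information. That is fair, and it is why they are given as up to about 65%.

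The motive is also limited. The quoted recommendation concerns people of 65 and over, everyone is offered the other vaccine free one to two years later, and section 5.1 describes both vaccines as having benefits and limitations. The caller demographics in section 4.3 allow some check on who was selected.

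Finally, a reader might infer that randomisation is undone. That goes too far. The in-depth work in Aims 2 and 3 contrasts high and low responders for each vaccine, which is not a randomised comparison and is less exposed. Section 8.1 plans propensity scores for gender, age, race and ethnicity, though not for health.

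**Conclusion.** The concern holds as a moderate, avoidable weakness in allocation concealment. It affects the randomised PCV13 v PPSV23 contrast. Its size is up to about 6.7 of 40 assignments certain and 65% guessable if assignments are known without delay. With a 7-day delay and uniform two-year accrual it is about 5.3 of 40 and 64%. These figures assume knowledge of the block length and full tracking of past assignments. Full predictability applies only if later lines of the Plan can be read, which the documents leave open. There is no evidence that anyone steered enrolment. Access to the Plan matters more than the block length, since 10 is already less guessable than the smaller sizes computed.

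**What to change.** **Main change.** Amend section 5.1 and the Visit 2 procedures in section 6.2 so that the Data Manager keeps the Plan. Only the current participant's assignment is released, after eligibility is confirmed and the number issued, by sealed envelope or database release. This replaces the nurse's look-up in the Plan. The same edit should state at which visit the assignment is disclosed, since section 5.1 points to eligibility (Visit 1) and section 6.2 to Visit 2. The cost is a wording change and a simple release step.

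**Secondary change.** For any numbers not yet used, generate the list with varied block sizes that are not printed in the protocol and not small, for example 8, 10 and 12. The gain is the removal of nearly all certain assignments. Average guessability stays at about 65%. The cost is one regenerated list and a final split that may differ slightly from 20:20. The protocol is at version 5.1 and does not say how many numbers remain unused, so the benefit of this second step cannot be judged from the documents.
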